6.2.3 Pharmacokinetics

Not applicable.

6.2.4 Biomarkers

Not applicable.

6.3 Study Procedures

The study procedures are detailed below.

6.3.1 Study Schedule

The total number of expected visits per participant is 6 visits. All participants will be given the option to participate in a 24 week therapeutic extension study of XRB treatment following completion of Visit 5 Week 8. If a participant elects to continue and/or initiate XRB treatment, there will be 12 total visits per participant. The average time needed to complete each visit will be approximately one hour. The initial week 0 screening and randomization visit will be conducted in a Rikers Island jail facility in the Opioid Treatment Program. Once consented, enrolled, and randomized, buprenorphine extended-release (XRB) or sublingual buprenorphine (SLB) daily maintenance will be provided per usual Opioid Treatment Program protocols in-jail and prior to release. The timing between randomization and release will vary. Typical misdemeanor sentences in NYC are 30-60 days, and participants may randomize at any time during this incarceration period, begin XRB vs. SLB treatment, and then leave jail after weeks-to-months. This variable, naturalistic, in-custody study period remains Study Week 0. Study Week 1 commences with the day of release from jail. Post-release, all study visits will be conducted at Bellevue Hospital Center's (BHC) Addiction Medicine clinic. Medical and research visits will be conducted weekly and then bi-weekly for both medication arms post-release (week 1 post-release, week 2, week 4, week 6, week 8). The medication schedule for both arms is as follows:

Buprenorphine Extended-Release: Participants randomized to this arm will receive at least two doses of XRB. The first will be administered at study week 0 in-jail, at least one week prior to release. Participants incarcerated for greater than 4 weeks following randomization will receive 2+ XRB doses prior to release. Post-release, XRB injections will be administered at study week 1-16 in the BHC Addiction Medicine clinic depending on the timing of the previous pre-release/community injections.

Sublingual Buprenorphine: Participants randomized to this arm will be provided SLB daily maintenance per usual Opioid Treatment Programs protocols in-jail. Post-release, SLB arm participants will receive follow-up care at Bellevue Hospital's Addiction Medicine or at non-BHC/NYU community providers, per their preference. We expect and will encourage most participants to follow-up at Bellevue, though this is not mandated. Typically an initial week's supply of SLB is prescribed within one week of release. At visit 2, week 2, SLB participants typically refill a two week's supply of daily maintenance SLB. SLB participants will continue to receive 2-4 week refill prescriptions for SLB from visit 2, week 2 through visit 6, week 8. Regardless of SLB prescribing patterns, they are encouraged to attend study follow-up visits at BHC per the same study schedule (Weeks 1,2,4,6,8). After the completion of Visit 5 Week 8, SLB participants will be offered XRB treatment in the 24 week therapeutic extension. If interested, participants would receive one or more XRB injections during the

period of Weeks 8, 12, 16, 20, 24, and 28 followed by a final safety documentation visit at Week 32.

For both treatment arms, urine toxicology tests will be conducted at all follow-up visits at the BHC Addiction Medicine Clinic in order to detect any illicit substance use as well as buprenorphine adherence.

STUDY SCHEDULE												
Test/Procedures	Screening/ Randomization	Treatment Period & Follow-Up					XR-B 20 Week Treatment & Follow-Up					
Study Visit Number	0	1	2	3	4	5	6	7	8	9	10	11
Week	0	1	2	4	6	8	12	16	20	24	28	32
Informed Consent ¹	X											
HIPAA ²	X											
Locator Form	X											
Medical History	X											
Psychological History	X											
Physician Progress Note	X	X	X	X	X	X	X	X	X	X	X	X
Confirm Eligibility	X											
Randomization	X											
Adverse Event Forms (AE, SAE, BUP specific AE)		X	X	X	X	X	X	X	X	X	X	X
Clinical Assessment of Intervention ³						X						X
Urine Toxicology		X	X	X	X	X	X	X	X	X	X	X
Pregnancy Test				X		X		X			X	
Demographics	X											
MOUD History/Preference	X											
ASI-Modified Lifetime/CJS-Baseline	X											
Timeline Followback	X	X	X	X	X	X	X	X	X	X	X	X
Inmate Lookup Form⁴		X	X	X	X	X						
New Arrests and Days Incarcerated Form⁴		X	X	X	X	X						
Overdose Form		X	X	X	X	X	X	X	X	X	X	X
XR-B Administration Form	X			X			X	X	X	X	X	

NYS Prescription Monitoring Data (SLB- Only)		X	X	X	X	X						
Dispense Study Medications⁵	X, #	X, #	X, #	X, #	X, #	X	X	X				
Treatment Retention		X	X	X	X	X						
Open-Ended Interviews⁶		X				X						
Qualitative Interviews⁷						X		X	X		X	
Treatment Satisfaction Form						X						X

Annotations:
 
 1. All patients must sign an informed consent consistent with ICH-GCP guidelines prior to participation in this trial, which includes performing any screening procedures, medication washout and any restrictions. 2. HIPAA authorization must be obtained on all patients participating in the study at Visit1. 3. Clinical Assessment must be completed per protocol instructions and by the treating investigator for that specific patient. 4. These instruments will be available for each visit, however they may/may not be filled out depending on participant's interaction with CJS 5. X = XRB, # = SLB; dispensation schedule varies depending on release date 6. Open-Ended interview should occur at participant's first & final community visit 7. For eligible XRB participants only, occurs at week 8 and final community visit. 												

6.3.2 Informed Consent

Potential participants interested in buprenorphine maintenance (currently a NYC jail standard of care) will be offered study information and encouraged to enroll. The study team will receive IRB-approval for all study documents, informational handouts, informed consent forms, informed consent quizzes, and all CRFs prior to screening and randomizing participants. Consent forms describing in detail the study agent, study procedures, and risks are given to the participant and written documentation of informed consent is required prior to starting intervention/administering study product. Written informed consent including a consent quiz adapted from the parent grant protocol will be used to document informed consent. Participants will have the opportunity to carefully review the written consent form and ask questions prior to signing. The participants may withdraw consent at any time throughout the course of the trial. A copy of the signed informed consent document will be given to the participants for their records. The rights and welfare of the participants will be protected by emphasizing to them that the quality of their medical care will not be adversely affected if they decline to participate in this study.

A copy of the signed informed consent document will be stored in the subject's research record. The consent process, including the name of the individual obtaining consent, will be thoroughly documented in the subject's research record. Any alteration to the standard consent process (e.g. use of a translator, consent from a legally authorized representative, consent document presented orally, etc.) and the justification for such alteration will likewise be documented.

6.3.3 Screening

Potential participants will meet with study staff to learn about study procedures, buprenorphine (XRB and SLB) treatment, and follow-up protocols. A pre-screen checklist will evaluate eligibility. All adult jail inmates with an upcoming release date, current opioid use disorder diagnosis, and currently maintained on sublingual buprenorphine-naloxone will be potential participants. If interested and eligible, participants will complete the informed consent process (ICF and ICF quiz). Once informed consent is obtained, baseline assessments will be administered prior to randomization. The baseline assessments include a drug and alcohol use history (ASI-Lite), demographics, a pre-arrest recall of drug and alcohol use (Timeline Followback), prior medication treatment for opioid use disorder exposure and preferences (MOUD Preference form), and jail Electronic Medical Record medical and psychiatric history and laboratory data, including HIV and HCV status.

6.3.4 Recruitment, Enrollment and Retention

Recruitment: Adult inmates with known Department of Corrections release dates and recent or on-going opioid treatment are housed in two NYC jail facilities, both on Rikers Island; the Eric M. Taylor Center (male) and the Rose M Singer Center (female). Approximately 150 persons a month leave this facility with an opioid use disorder diagnosis and on active OUD treatment (e.g. buprenorphine, methadone, naltrexone, or counseling). NYULMC study staff with NYC Health+Hospitals clinical credentials and HHC-approved access to Rikers electronic medical record database (EMR) will search for opioid dependent diagnoses, in-jail opioid treatment program participation and pending release dates of potential participants

Study Number s18-00823

located in this housing unit. Potential participants interested in buprenorphine maintenance (currently a NYC jail standard of care) will be offered study information and encouraged to enroll. As current daily maintenance of sublingual buprenorphine is required in order to be eligible for this pilot, participants will be already be affiliate with the in-jail Opioid Treatment Program and will be referred by the Opioid Treatment Program staff to Study Staff for further education about the trial and to schedule written informed consent and a comprehensive screening visit. Monetary compensation for time and travel are intended to facilitate and encourage follow-up visit attendance; transportation services for follow-up visits are otherwise not provided.

Informed Consent and Enrollment/Randomization: Study staff will obtain informed consent via the completion of the informed consent form and informed consent quiz. Consented and eligible participants will be randomized by sealed envelope or a web-based randomizer 1:1, XRB vs. SLB. Medications will be dispensed at the screening/randomization visit in-jail (visit 1, week 0) for both arms. All follow-up visits (visit 1-6) will take place at Bellevue Hospital Center's Addiction Medicine clinic and medication (XRB) will be provided free-of-charge.

6.3.5 On Study Visits

Screening and Randomization (~1.5 hours):

- Informed Consent & Informed Consent Quiz
- Baseline assessments:
 - Drug and alcohol use history (ASI-Lite)
 - Pre-arrest recall of drug and alcohol use (Timeline Followback)
 - Prior Medication Treatment for Opioid Use Disorder exposure & preferences (MOUD Preference form)
 - Jail Electronic Medical Record medical and psychiatric history & laboratory data, including HIV and HCV status
- Randomization envelope opened & completed by study staff and participant
 - Medication dispensed (XRB or SLB)
 - *Additional in-jail injections of XRB may occur if participant is incarcerated for over 4 weeks.*

Follow-Up Visits (v1-4, ~1 hour)

- Administrative data for SLB medication refills and post-release XRB injections
- Self-reported opioid and other drug use (Timeline Followback)
- Urine specimen collection and toxicology testing
- Adverse Event and Serious Adverse Event monitoring (SAFTEE)
- NYS Prescription Monitoring Data for community SLB pharmacy refill reporting
 - I-STOP/PMP Registry
- Treatment Retention Form completed
- *At visit 1 week 1, open-ended interview will be administered.*

- *At visit 3 week 4, second XRB administered, depending on prior injection date.*
- *At visit 3 week 4, pregnancy test will be administered..*

Research Visit 5 Week 8 (Final Visit, ~1 hour):

- Medication is not dispensed
- For participants electing to continue in the 24 week extension, initial and/or additional XRB injection could be administered at this time point
- Self-reported opioid and other drug use (Timeline Followback)
- Urine specimen collection and toxicology testing
- Pregnancy testing
- Treatment Retention completed
- Treatment Satisfaction completed
- Adverse Event and Serious Adverse Event monitoring (SAFTEE)
- NYS Prescription Monitoring Data for community SLB pharmacy refill reporting
 - I-STOP/PMP Registry
- Open-ended interview with participants concerning XRB vs. SLB treatment satisfaction and ease-of-use

Treatment Visit 6-10 Week 12, 16, 20, 24, 28 (~1 hour):

- 24 Week Extension Participants Only:
 - Self-reported opioid and other drug use (Timeline Followback)
 - Urine specimen collection and toxicology testing
 - Adverse Event and Serious Adverse Event monitoring (SAFTEE)
 - *XRB administered, depending on prior injection date.*
 - *At visit 7 week 16 and visit 10 week 28, pregnancy test will be administered*
 - *Qualitative Interviews (randomized to XRB treatment arm only) will be conducted at XRB injection treatment visits depending on participants' medication schedules.*

Safety Visit 11 Week 32 (~1 hour, final visit):

- Self-reported opioid and other drug use (Timeline Followback)
- Adverse Event and Serious Adverse Event monitoring (SAFTEE)
- Qualitative Interviews if applicable
- Treatment Satisfaction form

In-Jail Feasibility:

- Assessments of XRB vs. SLB
 - Logging the % eligible enrolling in the study
 - The density of medical/nursing/pharmacy visits per arm and per participant
 - Rates of medication diversion.

6.3.6 End of Study and Follow-up

After completion of the final visit (Visit 5, Week 8), study participation is complete for all participants who do not elect to continue and/or initiate treatment in the 24 week therapeutic extension of XRB treatment. All participants will be provided information on XRB and SLB and will be encouraged to continue treatment with the community opioid treatment provider of their choice. All participants will have the option of accessing services at Bellevue, including buprenorphine and methadone maintenance treatment. It is likely that the majority of participants in both arms will continue on SLB maintenance with the BHC Addiction Medicine clinic. XRB may become a usual care option at BHC during the course of this trial, depending on NYS Medicaid policies and H+H formulary updates.

For participants who continue in the 24 week therapeutic extension, after completion of the final safety visit (Visit 11, Week 32), study participation is complete. All participants will be provided the same information as highlighted above. It is likely that the majority of participants in this arm will continue on SLB maintenance with the BHC Addiction Medicine clinic.

In-jail feasibility will be assessed during and post study completion as the data is made available. All adverse event and serious adverse event monitoring (SAFTEE) will take place throughout the study and will be documented/reported as necessary.

6.3.7 Removal of subjects

Participation in this pilot, proof-of-concept, RCT is entirely voluntary and participants are free to withdraw at any time. In the event of early study termination, study staff will complete the study termination form, modeled from a CRF of the parent XOR study. Any participant withdrawing from the study prior to full study completion, regardless of study group, stands a risk of relapsing to illicit opioid or other drug/alcohol misuse. The study will assist with treatment referrals for detox services at Bellevue Hospital Center, but will not otherwise directly provide such services or medications. Otherwise any XRB or SLB patient who has relapsed and is not interested in continuing their baseline study condition (i.e., an XRB participant does not wish to continue injections due to side effects or for any other reason) will be encouraged to pursue other appropriate community treatment, the menu of which includes the robust addiction service offerings at Bellevue Hospital Center (BHC). BHC's services are available to all persons, regardless of insurance status or an ability to pay, and include emergency detox inpatient services, methadone treatment, office-based buprenorphine, and intensive outpatient and dual diagnosis programs. These services will consist of usual care occurring outside of the study and will not be directly provided by or paid for by the study.

6.4.1 Statistical Design

This pilot study is exploratory, and Aim 1 is a qualitative estimation of the feasibility and acceptability of this new form of buprenorphine in a large urban jail setting. The study will be moderately well-powered using a superiority contrast ($A \gg B$) of XRB vs. SLB surrounding Aim 2, retention in treatment post-release. Current rates of successful retention in community buprenorphine treatment immediately at one month post-release are 30% or lower (6). This current administrative data reflects closely results seen in an original BUP vs. methadone NYC jail RCT conducted in 2006-2008 (7). If XRB retention at one month post-release (Week 4) is 70% or greater, the study would be powered to detect a significant difference between arms. Analysis of treatment retention among XRB vs. SLB will consist of simple 2x2 tables for counts and proportions of weeks retained in treatment by arm. We are unlikely to extensively model and control for confounders or interaction terms.

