Rikers Island and the New York City Department of Corrections administered jail system in NYC is a prominent exception to US norms. NYC Health+Hospitals Division of Correctional Health Services, which administers all jail-based health care in NYC, and has a high-volume program for both continuing existing SLB patients through incarceration and initiating SLB in new patients prior to release. NYC jails provide an ideal setting in which to pilot jail-based use of newer extended-release buprenorphine compounds. Two members of NYC Health+Hospitals leadership, are key co-investigators in this proposal. This pilot will be a first of its kind evaluation of XRB in a criminal justice, underserved population at high risk or relapse and overdose.

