5.3.1 Number of Participants

N=50. A total sample size of N=50 would allow for an estimate of an Odds Ratio of 2.0-3.0 for the rate of persons successfully in community buprenorphine treatment at 4 weeks post-release (71% vs. 30% success favoring XRB; two-sided alpha of 0.05; 80+% power).

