6.4.2 Sample Size Considerations

A total sample size of $N=50$ would allow for an estimate of an Odds Ratio of 2.0-3.0 for the rate of persons successfully in community buprenorphine treatment at 4 weeks post-release (71% vs. 30% success favoring XRB; two-sided alpha of 0.05; 80+% power). The proposed sample size will not provide a definitive test of intervention efficacy, but is sized for feasibility testing.

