6.4.3 Handling of Missing Data

Follow-up among individual participants at Bellevue Hospital is encouraged with XOR's monetary incentives and tracking protocols. Participants in either arm choosing buprenorphine f/u at Bellevue will be particularly likely to complete follow-up. Administrative and program data covering community pharmacy fills of buprenorphine products and community provider reporting will be used to supplement treatment retention outcomes (Aim 2). Missing opioid urine toxicology data is considered MissingAsPositive.

7 - Trial Administration

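### Urines missed because a participant is back in jail are scored as illicit opioid use, and the custody data that the trial schedules are not used in any analysis rule

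*Combined protocol and SAP*

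**What the plan says.** **Clock and place.** Section 6.3.1 states that "Study Week 1 commences with the day of release from jail". Visits follow at Weeks 1, 2, 4, 6 and 8. The same section places all post-release study visits, and the follow-up urine tests, at the Bellevue clinic. Nothing pauses or stops the clock on re-arrest.

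**Missing urines.** Section 6.4.3: "Missing opioid urine toxicology data is considered MissingAsPositive". No reason for missingness is exempted.

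**Retention.** Section 6.4.1 plans "simple 2x2 tables for counts and proportions of weeks retained in treatment by arm". Section 6.4.2 sizes the trial on "persons successfully in community buprenorphine treatment at 4 weeks post-release". Section 6.1.5 names self-report, Bellevue records and prescription-monitoring audits as the sources for SLB retention after release. Section 6.4.3 adds community pharmacy fills and community provider reports.

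**Custody data.** The schedule table in 6.3.1 lists an Inmate Lookup Form and a "New Arrests and Days Incarcerated Form" at Weeks 1 to 8. Footnote 4 makes completion depend on contact with the criminal justice system. Section 7.5.1.1 lists both kinds of form as source documents. The measures named for the secondary aims in 5.2.2 and 6.2.1 include neither, and sections 6.4.1 to 6.4.3 do not mention custody.

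**Treatment in jail.** Section 3.2 describes a jail program that covers "continuing existing SLB patients through incarceration and initiating SLB in new patients prior to release".

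**The concern.** The participants have just left jail, and the trial plans to record new arrests, so some re-incarceration during the 8 weeks is foreseen. A person in custody cannot give a urine at Bellevue. Under 6.4.3 that urine is an illicit opioid positive, fixed by the rule and not by behaviour. If the person is released again and completes Timeline Followback, the same days may be reported as days without use. Sections 5.2.2 and 6.2.1 list both instruments without saying which one carries Aim 2, so the two could move in opposite directions.

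If re-arrest differed by arm, the difference would appear as a difference in opioid use. If it were equal, a true difference would be diluted.

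For retention the gap is one of wording. A re-jailed person may be taking buprenorphine without being in community treatment, and the analysis sentence in 6.4.1 does not say which of the two is meant.

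**Working it through.** **1. The plan's own figure.** The stated basis is "71% vs. 30% success favoring XRB; two-sided alpha of 0.05; 80+% power", with N=50 allocated 1:1, so 25 per arm. A two-sided pooled test of two proportions gives 84.8% power and Fisher's exact test gives 80.5%. The stated power reproduces.

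**2. Assumptions.** The documents give no re-arrest figure and no illicit-positive rate. For illustration:
- a share p of participants is re-jailed within 8 weeks, p = 5% to 30%;
- re-arrest is uniform over 56 days;
- the stay is uniform over 30 to 60 days (6.3.1 gives this range for typical misdemeanor sentences; applying it to every re-arrest is an assumption);
- 40% of those in the community are positive;
- no urine is missing for any other reason.

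**3. Probability of being in custody, given re-arrest.**
- Week 4: every stay exceeds 28 days, so anyone re-arrested by day 28 is still in custody: 28/56 = 0.50.
- Week 8: let u be the days from re-arrest to day 56. All with u < 30 are in custody, and a fraction (60 − u)/30 of the rest. This gives [30 + (30² − 4²)/60]/56 = 44.73/56 = 0.80.
- Mean share of the 56 days in custody: 0.469 by simulation.

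**4. Scored urine-positive rate.** Scored rate = 0.40 × (1 − c) + c, where c is the share of all participants in custody: c = 0.50p at Week 4 and 0.80p at Week 8.

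| Re-jailed by Week 8 (p) | In custody, Week 4 | Scored, Week 4 | In custody, Week 8 | Scored, Week 8 | Relative inflation, Week 8 |
|---|---|---|---|---|---|
| 5% | 2.5% | 41.5% | 4% | 42.4% | 6% |
| 10% | 5% | 43.0% | 8% | 44.8% | 12% |
| 20% | 10% | 46.0% | 16% | 49.6% | 24% |
| 30% | 15% | 49.0% | 24% | 54.4% | 36% |

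**5. Effect on the comparison at Week 8.** With equal custody in both arms, the scored difference is the true difference times (1 − 0.80p): 0.96 of it at p = 5% and 0.76 at p = 30%. If re-jailing were 10% in one arm and 20% in the other, with identical use, the scored rates would differ by 49.6 − 44.8 = 4.8 points.

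**6. Self-report.** If custody days enter Timeline Followback as days without use, use per calendar day falls by 0.469p: 2.3%, 4.7%, 9.4% and 14.1% for the four values of p. The direction is opposite to that of the urine score.

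**7. Retention at Week 4.** One person is 1/25 = 4 points of an arm. The expected number in custody per arm is 25 × 0.50p: 0.6, 1.25, 2.5 and 3.75. With 10% of each arm in custody (p = 20%), scoring them all as not retained gives 0.71 × 0.90 = 63.9% against 0.30 × 0.90 = 27.0%, pooled power 76%. Scoring them all as retained adds 10 points to each arm (73.9% against 37.0%), and power is again 76%. A uniform rule in either direction therefore costs about the same power; what changes is the meaning of the estimate.

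**The case against.** **Retention.** A reader might infer that weeks back in jail count towards retention, so that someone re-jailed on SLB is retained for all 8 weeks. The documents do not support that. Section 6.3.1 fixes when the clock starts, and 6.4.1 does not define the denominator. The aims in 4.1 and 4.3, the sizing statement in 6.4.2 and the sources in 6.1.5 and 6.4.3 all refer to community treatment, and no jail dosing record is named as a retention source. This stands: the remaining gap is one of wording.

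**Opioid use.** A reader might also infer that one outcome can be scored both opioid-free and opioid-positive. It cannot. The urine score is determinate, and the conflict is between two instruments. No section sets custody days to zero on Timeline Followback, and a true report of no use in jail is accurate. What survives is that the urine rule assigns illicit use to people documented to be in custody.

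**Completeness of the forms.** Footnote 4 does not guarantee completion, and the forms are scheduled at visits that a re-jailed person cannot attend. Custody dates may therefore be incomplete. The Treatment Retention Form is not reproduced in the documents and could contain a rule.

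**Size.** Every magnitude rests on assumed rates. If re-jailed people would otherwise have been positive more often, the overstatement shrinks. At an assumed 70% it is 0.80p × 0.30 = 0.24p, or 1.2 to 7.2 points, against 0.48p, or 2.4 to 14.4 points, at 40%. Custody that begins after Week 4 does not touch the powered contrast. The 30% benchmark may already count re-jailed people as failures, in which case the power loss in step 7 is overstated.

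**Importance.** The primary objective is feasibility, and 6.4.2 disclaims a definitive efficacy test. This limits the weight of the point, but it does not justify leaving the rule unstated.

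**Conclusion.** The point holds for the urine outcome. Followed as written, 6.4.3 records illicit opioid use for participants in jail at a scheduled visit, and the custody forms that could identify them play no part in the analysis. For retention the defect is narrower: 6.4.1 omits the word that the rest of the protocol supplies.

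The size is unknown because the documents give no re-arrest rate. Under the assumptions in step 2, a 40% community rate is scored as 42-54% at Week 8 when 5-30% are re-jailed. Bias in the urine comparison towards one arm needs custody to differ between the arms, which is possible but not shown; equal custody only dilutes a difference. This is an inexpensive improvement to secondary analyses and does not threaten the primary feasibility objective.

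**What to change.** 1. **Section 6.4.3.** Flag urines missed because of documented custody. Report the opioid outcome by arm both with and without counting them as positive.
2. **Section 6.4.1.** State that retention means retention in community treatment. Keep re-jailed participants in the all-randomised Week 4 denominator as not in community treatment, and tabulate re-incarceration by arm.
3. **Supportive analysis.** Show Timeline Followback use per day in the community, with days incarcerated by arm.

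**Cost.** A few sentences and one or two extra tables, using forms already scheduled. Custody occurs after randomisation and may be affected by treatment, and the forms may be incomplete. The custody-adjusted figures should therefore be labelled supportive, and the all-randomised Week 4 comparison should remain the main retention analysis. The number of participants whose custody dates are unknown should be reported with the tables.
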